5.2.5 Efficacy Endpoints Calculation

5.2.5.1 Numeric ACR (ACR-N) Index

The numeric ACR (ACR-N) will be derived by the sponsor for Visits 3 through 7 based on the ACR core set measures collected by the Investigator. See Section 3.5.6.1 of the protocol for the description of the ACR core set measures assessments by the Investigator.

This is a continuous variable expressing the percentage improvement from baseline a subject has experienced, defined as the minimum of percent improvement in swollen joints, tender joints and the median percent change in the other five ACR core set measures:

1. Subject's Assessment of Arthritis Pain.
2. Subject's Global Assessment of Disease Activity.
3. Physician's Global Assessment of Disease Activity.
4. Health Assessment Questionnaire Disability Index
5. Acute phase reactant (hs-CRP)

Thus, an ACR-N of X means that the subject has achieved a change of at least X% in the tender and swollen joint counts and a change of at least X% in the median of the other five other parameters. Numeric ACR will take a negative value if there is a worsening in either the swollen joint count, tender joint count and the median of the other five ACR core set measures (i.e., a subject can have a negative ACR-N despite improving in two of the three components).

5.2.5.2 The ACR20/50/70 Response Rate

The ACR20/50/70 response rate will be calculated by the sponsor for Visits 3 through 7 based on the ACR core set measures collected by the Investigator.

This composite parameter measures improvement in tender (68) and swollen (66) joint counts and improvement in at least three of the following five ACR core set measures as listed above.

The ACR20/50/70 response rate is a dichotomous variable with a positive (= responder) or negative (= non-responder) outcome.

ACR20 is $\geq 20\%$ improvement

ACR50 is $\geq 50\%$ improvement

ACR70 is $\geq 70\%$ improvement

5.2.5.3 Simple Disease Activity Index (SDAI)

The SDAI will be calculated by the Sponsor for all study visits. See Section 3.5.6.1.2 of the Protocol for the list of 28 joints included in the SDAI scoring.

The scoring of SDAI will be done as follows:

Variable	Range
Tender joint score	(0-28)
Swollen joint score	(0-28)
Patient global score	(0-10)
Provider global score	(0-10)
C-reactive protein (mg/dL)	(0-10)
Add the above values to calculate the SDAI score	(0-86)

Interpretation of scoring will be done as follows:

SDAI Score Interpretation	
0.0-3.3	Remission
3.4-11.0	Low Activity
11.1-26.0	Moderate Activity
26.1-86.0	High Activity

5.2.5.4 Clinical Disease Activity Index

The CDAI will be calculated by the Sponsor for all study visits. See Section 3.5.6.1.2 of the Protocol for the list of 28 joints included in the CDAI scoring.

The scoring of CDAI will be done as follows:

Variable	Range
Tender joint score	(0-28)
Swollen joint score	(0-28)
Patient global score	(0-10)
Provider global score	(0-10)
Add the above values to calculate the CDAI score	(0-76)

Interpretation of scoring will be done as follows:

CDAI Score Interpretation	
0.0-2.8	Remission
2.9-10.0	Low Activity
10.1-22.0	Moderate Activity
22.1-76.0	High Activity

5.2.5.5 Disease Activity Score (DAS) 28

The DAS assessment is a derived measurement with differential weighting given to each component. The DAS 28 (CRP) will be calculated by the Sponsor at all study visits. See Section 3.5.6.1.2 of the Protocol for the list of 28 joints included in the DAS calculation.

The components of the DAS 28 arthritis assessment include:

1. Tender/Painful Joint Count (28)
2. Swollen Joint Count (28)
3. CRP
4. Subject's Global Assessment of Disease Activity

The DAS 28 will be calculated using the following formula:

$$\text{DAS28(CRP)} = 0.56 \times \sqrt{(\text{TJC28})} + 0.28 \times \sqrt{(\text{SJC28})} + 0.36 \times \ln(\text{CRP}+1) + 0.014 \times \text{SGA} + 0.96$$

5.2.5.6 Percentage of Subjects achieving Boolean Remission

This secondary efficacy parameter will be calculated by the Sponsor, based on the following definition:

- Tender joint count (TJC) (28) ≤ 1
- Swollen joint count (SJC) (28) ≤ 1
- C-reactive protein ≤ 1 mg/dL
- Subject's global assessment (SGA) of disease activity ≤ 1 (on a 0 - 10 scale)

5.2.5.7 EULAR Response Criteria

The EULAR response criteria will be assessed by the Sponsor.

This parameter considers both the change in DAS28 between two time points, as well as DAS28 value at a specific time point.

DAS28-CRP will be utilized in calculating the EULAR response in the study subjects.

DAS28 improvement →			
Present DAS28 ↓	>1.2	>0.6 and ≤ 1.2	≤ 0.6
≤ 3.2	good response	moderate response	no response
>3.2 and ≤ 5.1	moderate response	moderate response	no response
>5.1	moderate response	no response	no response

5.2.5.8 HAQ-DI Score and Calculation

The HAQ-DI's scoring conventions allow for the computation of two disability indices:

1. The Standard HAQ-DI is the preferred and traditional scoring method, which considers the use of aids/devices.
2. The Alternative Disability Index does not consider the use of aids/devices.

A subject must have a score for at least six of the eight categories. Otherwise a HAQ-DI score cannot be validly computed. For this study, the standard computing method will be applied.

Computing the Standard HAQ-DI Score (With Aids/Devices): There are three steps:

1. Sum the 8 category scores by using the highest sub-category score from each category (for example, in the category “EATING” there are three sub-category items. If a subject responds with a 1, 2 and 0, respectively; the category score is 2).
2. Adjust for use of aids/devices and/or help from another person when indicated. Table 2 identifies the Aid/Devices companion variable for each HAQ-DI category.

Table 2. Companion Aids/Device Items for HAQ-DI Categories

HAQ-DI Category	Companion Item
Dressing & Grooming	Devices used for dressing
Arising	Built up or special chair
Eating	Built up or special utensils
Walking	Cane walker, crutches, wheelchair
Hygiene	Raised toilet seat, bathtub seat, bathtub bar Long handled appliances in bathroom
Reach	Long handled appliances for reach
Grip	Jar opener (for jars previously opened)

- Adjust the score for a category by increasing a zero or a one to a two.
 - If a subject's highest score for that sub-category is a two it remains a two, and if a three, it remains a three.
3. Divide the summed category scores by the number of categories answered (must be a minimum of 6) to obtain a HAQ-DI score of 0-3 (3=worst functioning)
 4. If any component in HAQ-DI derivation is missing and HAQ-DI cannot be derived, no imputation will be done, and HAQ-DI will be left as missing.

5.3 Safety Parameters

5.3.1 Adverse Events (AEs)

The Medical Dictionary for Regulatory Activities (MedDRA) Version 21.0 will be used to map verbatim AEs to preferred terms and their respective primary system organ classes. However, a different (non-primary) system organ class may be selected where appropriate after a medical review of the mapping. Adverse events will be characterized as either pre-treatment or treatment-emergent according to the criteria described in the following sections.

5.3.2 Pre-treatment Adverse Events

A pre-treatment AE is one with an onset date prior to the date of the first dose of study drug.

For an AE occurring on the day of first dose, all AEs occurring on the day of first dose will be considered as TEAE when the time of AE occurrence relative to the dosing is unknown.

5.3.3 Treatment-Emergent Adverse Events

A treatment-emergent AE is defined as any AE with an onset date on or after the first dose of study drug, provided that this AE did not previously occur during the pre-treatment period (i.e., before the first dose of study drug taken after randomization). However, a pre-treatment AE can become treatment-emergent if it continued from the pre-treatment period but worsened after the first dose of study drug or it stopped and re-occurred (a new onset time) with a worsen severity after the first dose of study drug.

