- A PPD test is considered positive if, at 48 to 72 hours of administration, the induration (not erythema) obtained is ≥ 5 mm.
- If the quantiFERON[®]-TB Gold-In-Tube test is performed and it is indeterminate, a retest is allowed if results can be obtained in time prior to Visit 2. If the retest results are also indeterminate, the PPD test may be performed (unless the subject has a history of BCG vaccination) and, if negative, the subject may be randomized into the study.
- The quantiFERON[®]-TB Gold-In-Tube test should not be performed within ≤ 4 weeks from the date of a live vaccination.
- Subjects who have had contact with a person with active tuberculosis are excluded, unless documentation of appropriate completion (>12 weeks prior to the Screening Visit) of tuberculosis prophylaxis is provided to the investigator.

12. History of live attenuated vaccination within 6 weeks prior to Day 1 (Visit 2), or have a live attenuated vaccination planned during the course of the study or within 6 weeks after the last dose of study drug;

13. Have donated or received any blood or blood products within 8 weeks prior to the Screening Visit (Visit 1);
14. History of a clinically-significant infection (e.g., required oral antimicrobial or antiviral therapy) within 8 weeks prior to Day 1 (Visit 2), except for treated urinary tract infections, which will be permitted if resolved >1 week prior to Day 1 (Visit 2);
Note: Subjects with confirmed Zika infection within 4 weeks **prior to the Screening Visit (Visit 1)** are prohibited to participate in the study, whether or not they have received antiviral therapy.
15. History of opportunistic infections or infection requiring hospitalization or parenteral antibiotic, antiviral, antifungal, or antiparasitic therapy within 6 months prior to Day 1 (Visit 2) or any history of recurrent infections or conditions predisposing to chronic infections (e.g., bronchiectasis, chronic osteomyelitis);
16. History of shingles within 12 months prior to the Screening Visit or any known history of disseminated/complicated herpes zoster;
17. History of acute inflammatory joint disease of an origin other than RA or subject has any other rheumatic disease other than RA (e.g., any arthritis with onset prior to age 16 years, gout, mixed connective tissue disease, seronegative spondylarthropathy, psoriatic arthritis, reactive arthritis or systemic lupus erythematosus) or fibromyalgia;

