6.5.1 Adverse Events (AEs)

The number and percentage of subjects experiencing TEAEs will be tabulated by treatment according to the following categories:

- Overall summary of TEAEs.
- TEAEs by system organ class and preferred term.
- TEAEs leading to study discontinuation by system organ class and preferred term.
- TEAEs by system organ class, preferred term and AE severity.
- TEAEs by system organ class, preferred term and AE causality.
- TEAEs by preferred term (in order of descending frequency in the total JTE-051 group).
- Serious AEs (SAEs) by system organ class and preferred term.
- Serious AEs leading to study discontinuation by system organ class and preferred term.

Listings will be provided for SAEs and AEs leading to study discontinuation.

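### The SAP's treatment-emergent rule leaves out a screening adverse event that resolves and restarts on study drug without worsening, so the TEAE tables slightly undercount recurrences

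*SAP*

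**What the plan says.** SAP 5.3.1 sets up two classes: "Adverse events will be characterized as either pre-treatment or treatment-emergent according to the criteria described in the following sections".

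SAP 5.3.2 defines the first class by onset date alone: "A pre-treatment AE is one with an onset date prior to the date of the first dose of study drug".

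SAP 5.3.3 defines the second as "any AE with an onset date on or after the first dose of study drug", with the proviso "provided that this AE did not previously occur during the pre-treatment period". It then gives two routes by which a pre-treatment event can become treatment-emergent:

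- it was ongoing: "it continued from the pre-treatment period but worsened after the first dose of study drug";
- it had resolved: "it stopped and re-occurred (a new onset time) with a worsen severity after the first dose of study drug".

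SAP 6.5.1 introduces the adverse event tables with "The number and percentage of subjects experiencing TEAEs will be tabulated by treatment according to the following categories". Most of the lines that follow are labelled TEAE, including the one for discontinuations. Two lines are labelled as serious AEs without the words treatment-emergent. Listings of SAEs and of AEs leading to discontinuation are also planned. SAP 7 lists all collected data by subject.

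Protocol 3.6.3 starts adverse event collection at informed consent. Protocol 3.2 allows a screening period of up to 28 days, with defined extensions. Protocol 3.6.2 rates severity as mild, moderate or severe, separately from seriousness.

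**The concern.** The proviso removes any event with a recorded pre-treatment occurrence, and the route back for a resolved event requires higher severity. An event that had cleared before dosing and starts again during treatment is a new on-treatment onset. The rule nevertheless leaves it out of the tables that carry the between-arm safety comparison, unless the investigator rates it higher on a three-level scale.

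At stake is the incidence of recurrent events by preferred term, and the table of TEAEs that led to discontinuation. If the drug makes such events more likely to return, the uncounted events are part of the drug effect, and the observed difference from placebo shrinks.

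The proviso also does not say whether the same AE is matched on verbatim term, preferred term or diagnosis. Matching on preferred term would widen the exclusion.

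**Working it through.** This is a classification rule with no stated figure to reproduce, so the check is to apply SAP 5.3.2 and 5.3.3 literally to every case.

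**Inputs.** On-treatment severity has 3 levels (Protocol 3.6.2). The history is either no prior event, or a prior event of 3 possible severities that was ongoing or resolved at first dose. That gives 3 combinations without a prior event, 3 × 3 = 9 with an ongoing one, and 3 × 3 = 9 with a resolved one that recurs.

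| History at first dose | Combinations | Treatment-emergent | Pre-treatment only | Neither |
|---|---|---|---|---|
| No prior event | 3 | 3 | 0 | 0 |
| Prior event ongoing | 9 | 3 (worsened) | 6 | 0 |
| Prior event resolved, then recurs | 9 | 3 (worsened) | 0 | 6 |

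The 6 unclassified patterns are 3 at the same severity and 3 at lower severity. The counts show where the gap lies. They are not probabilities, because the patterns are not equally likely.

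**Comparison with SAP 6.5.** For potentially clinically significant (PCS) laboratory, vital-sign and ECG values, baseline is the last non-missing value before first dose. A PCS value on treatment counts if baseline was normal or missing. Worsening is required only when baseline was itself a PCS value. The two rules compare as follows:

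- Abnormal at screening, normal at baseline, abnormal again on drug: counted.
- Clinical event during screening, resolved before dosing, back on drug at the same severity: not counted.

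The PCS rule applies the worsening test to a state present at baseline. SAP 5.3.3 applies it also to one that had gone, and gives no reason for the difference.

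**Size.** One subject in a planned arm of 50 is 1/50 = 2 percentage points. The documents give no recurrence rates, so the rest is illustration on assumed inputs, per event term:

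- q, the share of subjects with a resolved screening event of that term: 2% to 10%
- r, the share of those who recur on drug: 10% to 30%
- w, the share of recurrences that are no worse: 50% to 100%

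Subjects lost = n × q × r × w.

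- Per 50-subject arm: 50 × 0.02 × 0.10 × 0.5 = 0.05, up to 50 × 0.10 × 0.30 × 1.0 = 1.5.
- Across the 200 active subjects: 200 × 0.02 × 0.10 × 0.5 = 0.2, up to 200 × 0.10 × 0.30 × 1.0 = 6.

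**After the change proposed below.** All 9 resolved-then-recurring patterns become treatment-emergent, so the unclassified count falls from 6 to 0. Ongoing events are unaffected, with 3 of 9 still counted.

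**The case against.** **The event may simply remain pre-treatment.** SAP 5.3.3 speaks of a pre-treatment AE that can become treatment-emergent, so a programmer could leave a non-worsened recurrence in the first class, and the two-class scheme would hold. This reading conflicts with the onset-date rule in 5.3.2, because the recurrence has its own later onset. It also leaves the event out of the TEAE tables, so the undercount stands on either reading.

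**Counting only worsening is a deliberate and common-sense choice.** It keeps fluctuating background symptoms out of the tables, and Protocol 1.3 expects musculoskeletal complaints to be common. That is a fair reason for the test on ongoing events, and a real cost of dropping it for resolved ones. It does not explain the different treatment of PCS values.

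**A reader might infer that repeat infections on drug go uncounted.** The documents do not support that as a general statement. First infections on drug are all counted. Exclusion criteria 14 and 15 bar most recent clinically significant infections and any history of recurrent infections. Criterion 14 admits treated urinary tract infections resolved more than 1 week before Day 1, but one that began before consent is not an adverse event in the study database. Only an infection that starts after consent and clears in time triggers the rule. With a 28-day screening period that window is about 28 − 7 = 21 days. It is a valid but narrow example. Nor does the visible text rank infection as the main risk: Protocol 1.3 names infections and malignancies together as examples.

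**A reader might infer that serious recurrences disappear.** That is not established. The SAE lines in SAP 6.5.1 are not labelled treatment-emergent, although the introductory sentence is, so a serious recurrence may be tabulated. It should in any case appear in the SAE listing, and all data are listed under SAP 7.

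**The effect is small.** This stands. The magnitude is wholly assumed. Subjects with a resolved screening event should be balanced across arms by randomization. An affected subject still enters the overall TEAE count through any other TEAE.

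**Conclusion.** The point holds as a gap in the definition with a limited effect. By the text of SAP 5.3.1 to 5.3.3, a post-consent event that resolves before dosing and restarts on drug at the same or lower severity belongs to neither class. It is absent from the TEAE incidence and TEAE-discontinuation tables, though not from the listings.

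The consequence is a small undercount of recurrent events in every arm: 2 percentage points per lost subject in an arm of 50, and about 0.05 to 1.5 subjects per arm per event term under the assumed rates above. Bias in the drug-placebo difference would arise only if treatment changes how often such events return, on which the documents are silent. The conclusion about classification does not depend on the assumed rates; only the size does.

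The definition should be corrected because it is internally incomplete and out of line with the SAP's own PCS rule. It does not show that the infection or serious-event comparison is unsound.

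**What to change.** Rewrite SAP 5.3.3 so that a TEAE is either:

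- (a) any AE with a new onset at or after the first dose, including the return, at any severity, of a pre-treatment event that had resolved; or
- (b) an AE ongoing at first dose that afterwards worsens in severity.

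Delete the proviso about previous occurrence and the worsening condition for events that stopped and came back. The rule in 5.3.2 for events on the day of first dose with unknown timing can stay. With the proviso gone, no term-matching rule is needed for recurrences. No separate criterion for events that become serious is needed to close this gap.

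The cost is one SAP sentence and one derivation line, applied to all arms and best settled before the randomization code is released. The downside is slightly higher TEAE counts in every arm, placebo included, some of which will be fluctuating background symptoms.

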5.3.4 Medical History

A complete medical history will be obtained at the Screening Visit (Visit 1) and will include evaluations for past or present conditions. [REDACTED]

Stable or improving pre-existing conditions that are detected as part of the screening procedures (e.g., ECG, physical examination, [REDACTED] vital signs and laboratory test abnormalities) are medical history.

5.3.5 Study Medication Compliance

Total number of tablets taken will be recorded in the eCRF for the corresponding intervals as scheduled in [Table 1](#). Compliance of the study medication will be calculated as follows:

$$\text{Compliance (\%)} = \frac{\text{Total tablets taken}}{\text{Treatment duration} \times 4} \times 100\%$$

Compliance will be calculated for both the treatment duration between visits and the entire treatment period.

5.3.6 Clinical Laboratory Results

Hematology, coagulation, serum biochemistry, bone-specific alkaline phosphatase, lipid profile and urinalysis are collected as scheduled in [Table 1](#). The following information will be

derived for each of the hematology, coagulation, serum biochemistry, urinalysis and other parameters:

- Change from baseline at all post-baseline visits
- Classification relative to the normal range ('Low', 'Normal' or 'High')
- Treatment-Emergent potentially clinically significant (PCS) abnormalities, if applicable

Abnormalities in liver tests will be identified.

In addition, 25-hydroxyvitamin D, rheumatoid factor (RF), anti-cyclic citrullinated peptide (anti-CCP) antibodies and serum immunoglobulins G, M and A (IgG, IgM and IgA), viral serology, drugs of abuse and alcohol screen, pregnancy test and follicle stimulating hormone will also be obtained at the corresponding scheduled visit, respectively.

5.3.7 Vital Signs

Vital signs and body weight are collected as scheduled in [Table 1](#). Vital signs include systolic/diastolic blood pressure, pulse rate, respiratory rate and body temperature (°C). Subjects must rest in a sitting position for at least 5 minutes in preparation for blood pressure and pulse rate assessments. The following information will be derived for all vital signs and body weight:

- Change from baseline at all post-baseline visits
- Treatment-emergent PCS abnormalities, if applicable

5.3.8 12-Lead ECG

Twelve-lead ECG recordings and conduction intervals including RR, PR, QRS, QT are obtained according to the schedules summarized in [Table 1](#). The Fridericia-corrected QT interval (QTcF) (Fridericia's formula, QTcF = QT/RR^{1/3}) will be calculated and reported. The following information will be derived for each of the 12-lead ECG measurements:

- Change from baseline to all post-baseline visits
- Treatment-emergent PCS abnormalities, if applicable

The overall clinical interpretation of an ECG is assessed as follows: normal, abnormal not clinically significant or abnormal clinically significant.

5.3.9 Physical examination

Physical examination is conducted as scheduled in [Table 1](#). The physical examinations include examination of the following body systems: general appearance, skin (including hair and nails), HEENT (head, ears, eyes, nose, throat), neck/thyroid, chest/lungs, cardiovascular, gastrointestinal (GI), [REDACTED] psychiatric/emotional, lymphatic and musculoskeletal. Clinically significant abnormal physical examination findings will be recorded as medical history or AE where appropriate.

5.4 Pharmacokinetic (PK) Parameters

Trough concentrations of JTE-051 are measured from visit 3 to visit 6 during the treatment period.

The relationship between the JTE-051 dose (exposure) and response will be assessed (exploratory).

